#### **EVALUATION OF PRODUCT SUPERIORITY**

The primary outcome of total number of blood components (RBCs, platelets, plasma) used over the admission within the first 30 days after surgery will be evaluated using a two-sample t-test on the log-transformed values or the Wilcoxon rank-sum test if the log-transform does not result in an acceptable comparability to a normal distribution. This will be based on an intent-to-treat paradigm (all subjects randomized will be evaluated and in the group they were randomized to). However, it is assumed that all of the subjects will be appropriately evaluated for this endpoint.

There are a number of secondary endpoints, and the specific statistical method is indicated below:

- 1. Number of cryo or fibrinogen concentrate products used perioperatively (defined as anesthesia start to 24 hours post-procedure): Wilcoxon rank-sum test
- 2. Number of RBC, plasma, and platelet products used perioperatively (defined as anesthesia start to 24 hours post-procedure): Wilcoxon rank-sum test
- 3. Time from cryo order to ready in the blood bank: Wilcoxon rank-sum test
- 4. Time from cryo order to start of infusion: Wilcoxon rank-sum test
- 5. Number of cryo units wasted by blood bank per day during study periods: Wilcoxon rank-sum test
- 6. Laboratory measures for cryo and PR cryo (pre and post transfusion FIBTEM amplitude at 10 mins and maximum clot firmness, fibrinogen): Wilcoxon rank-sum test
- 7. Volume in mediastinal drains (e.g. chest tube for CV surgery) at 24 hours (or until removed): Wilcoxon rank-sum test
- 8. Length of stay (OR, ICU and hospital) & time on ventilator: log-rank test, particularly if there is any censoring
- 9. Overall cost of cryo vs PR cryo, when factoring wastage, during each 1-month period: Wilcoxon rank-sum test
- 10. Fibrinogen level most proximal to end of procedure, with adjustment for fibrinogen dose administered (if known): without adjustment the Wilcoxon rank-sum test can be used; with adjustment a properly selected linear model (depending on the link function required)

[figure not shown]
In order to control statistical significance for this number of endpoints, the Holm procedure will be used.

[figure not shown]
Many of the endpoints noted above can be evaluated after adjustment with selected covariates using a properly selected linear model (depending on the link function required).

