### **STUDY DESIGN**

Given that PR cryo can be more readily available for urgent perioperative need, the transfusion medicine service and anesthesiologists at NYP/WC would like to transition to this product. PR cryo is a more expensive product, so it is necessary to evaluate whether its availability will reduce the need for other blood products or reduce traditional cryo wastage, prior to fully converting to this product. A single center prospective, pilot cluster randomized study with an adaptive design will be used to compare the availability and cost effectiveness of cryo and PR cryo when it is ordered for standard clinical indications. In this design, the intervention and randomization are not made at the level of the individual patient, but rather on clusters of patients by month. The clusters will include all patients at NYP/WC for whom pooled cryo is ordered during a single month, not just liver transplant and cardiovascular surgery patients.

Since both products are considered clinically equivalent, the blood bank will alternate use of PR cryo and regular cryo each month for all patients with a cryo order over a one year period during the transition to the use of this new product. All patients will receive either traditional cryo or PR cryo in a given month; however, only a subset (CV and LT patients) will be studied.

Data from the EMR and lab systems will be collected from the NYP data warehouse during the one-year QA study and included in the data analysis. The following demographic variables will be collected: age, ethnicity, race, gender, underlying diseases, surgery type, medications given within 5 days of surgery.

The primary outcome will be the total number of blood components (RBCs, platelets, plasma) used over the admission within the first 30 days after surgery.

REDCap will be used for data collection/storage. Our data scientist, who is an Epic Clinical Data Navigator (CDN), will use SQL queries through the NYP Jupiter data warehouse for automated data extractions of clinical and laboratory data. A TRAC request will be submitted once the IRB is approved. Any variables not available through Jupiter will be extracted manually from the electronic medical record by the research coordinator and entered manually in REDCap. We will use the Safe Harbor method for de-identification of data. We will remove all 18 PHI elements referenced by HHS that could identify a patient.

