### STATISTICAL ANALYSIS

#### RATIONALE FOR A CLUSTER RANDOMIZED TRIAL

Individual patient efficacy clinical trials are useful to establish the clinical efficacy of an intervention amongst a carefully selected population under optimal conditions following detailed protocols. However, such trials do not address questions about how an intervention or logistical change affects clinical practice in the real world.

The surgical care of patients in our hospital is undertaken using standardized procedures that optimize outcomes, such as standard preoperative assessment and pre-and postoperative care pathways. Because our cardiac surgery and liver transplant services deliver care through standard institutional policies, it is appropriate to address whether either of the two FDAapproved blood products for fibrinogen replacement in acquired hypofibrinogenemia used during surgery to treat bleeding would reduce the total amount of blood products transfused. Testing the effects of the two products mandates a pragmatic trial done with randomization of product used by month rather than by patient. It is extremely difficult to predict which patients will receive fibrinogen replacement during surgery and thus impossible to predict which patients to consent ahead of time. At the time the decision is made to transfuse cryoprecipitate, a patient is already bleeding and under anesthesia, and thus there is no opportunity to consent in real time. Thus, this study will use a cluster randomization treatment assignment design with a calendar month time period as the cluster; specifically addressing whether the use of cryoprecipitate or PR cryoprecipitate reduces overall blood transfusions without any contamination of study groups by the inability to fulfill the appropriate cryo use if individual randomization had been used.

The main challenge of a cluster-randomized trial is the need for inflated sample size (relative to a non-clustered design) that results from clustering. Individuals within a cluster tend to have a smaller degree of variation compared to the variation between clusters, which is measured statistically by the intra-cluster correlation coefficient (ICC) (Arnup SJ et al). If the ICC is greater than 1, then this cluster effect will incorrectly reduce the standard error of the model estimates

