if it is not properly accounted for in the analysis. This study will use randomization between intervention arms each month with a design known as the cluster randomized trial. This allows for the ability to assure that all research subjects in a given month will receive a particular cryo product and ensure the reduction in contamination of the two study arms (one of the primary reasons for designing studies in this fashion). In the planned trial, each month the Weill Cornell blood bank will be randomized to one of the two cryoprecipitates as part of a quality improvement study, the randomized product will be used as standard institutional policy for an entire calendar month. At the end of each month, the blood bank is re-randomized to a new standard policy that is used for the subsequent calendar month. This design is methodologically rigorous and tests the effect of a change in standard policy as it would actually be used in the clinical setting.

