#### **SAMPLE SIZE ANALYSIS**

The primary endpoint of the study is total number of blood components other than cryo (RBCs, platelets, plasma) used over the hospital admission within the first 30 days after surgery. The goal of the trial is to demonstrate a 20% reduction in this total blood product use for PR cryo compared to the total observed with conventional cryo. In order to determine this effect size and the patient variability associated with this outcome, data were collected from 150 cardiovascular surgery and liver transplant cases at the study center during 6 months in 2021. Because the number of units used was clearly right-skewed and, therefore, possibly lognormally distributed, the sample size determination was based on the hypothesized ratio of means (effect size) of 0.8. In addition, the coefficient of variation is the key determinant of variability with log-normal data, and this was seen with the recent data to be a value of 1.1. The other issue to consider in this calculation is the cluster randomization. However, the cluster in this study is the month when the surgery is performed. The assumption is made that the intracluster correlation of the primary outcome within a given month should be very small, say 0.0001. As a result, this would have very little effect on the sample size (the Kish design effect is about 1.01 assuming approximately 100 subjects per month). Then with 80% power and 5% significance (two-sided), the number of subjects per group would be 251.

However, there is a possibility that the effect size has been overestimated. Thus, a sample size re-estimation will be conducted after 60% of the subjects have been included in the trial. The method of Gould (Gould AL. Interim analyses for monitoring clinical trials that do not materially affect the type I error rate. Stat Med 1992; 11:55-66.) will be used to re-evaluate the sample size.

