### **INTERIM ANALYSIS**

A separate interim analysis for futility will be conducted on the primary endpoint when 60% of the subjects have completed the trial. Sixty percent of 502 (251 per group) is 302. We expect to accrue 302 patients in approximately 1 year. During the interim analysis we will decide if the study will continue or stop. This will involve the calculation of conditional power and a potential stopping rule of a value for this calculation of <10%.

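### Product is assigned by calendar month, but the primary test treats patients as independent, so its 5% error rate rests on an unsupported month ICC of 0.0001

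*Combined protocol and SAP*

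**What the plan says.** The section Rationale for a Cluster Randomized Trial makes the calendar month the cluster: "At the end of each month, the blood bank is re-randomized to a new standard policy". It also states the consequence of clustering: "If the ICC is greater than 1, then this cluster effect will incorrectly reduce the standard error of the model estimates", and the sentence goes on "if it is not properly accounted for in the analysis".

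Under Evaluation of Product Superiority, the primary outcome "will be evaluated using a two-sample t-test on the log-transformed values or the Wilcoxon rank-sum test". The patient-level secondary outcomes are likewise given Wilcoxon or log-rank tests. No month effect, GEE, cluster-robust variance or month-level test of the primary outcome is named.

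Clustering is handled only under Sample Size Analysis, where "the intracluster correlation of the primary outcome within a given month should be very small, say 0.0001" and "the Kish design effect is about 1.01 assuming approximately 100 subjects per month".

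Two related statements do not agree with these. Study Design says "the blood bank will alternate use of PR cryo and regular cryo each month", which is not re-randomization. Interim Analysis says "We expect to accrue 302 patients in approximately 1 year", which is about 25 per month, not 100.

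**The concern.** When a whole month receives one product, any difference between months that has nothing to do with the product, such as case mix or staffing, is shared by every patient in that month. A patient-level test counts this shared variation as if it were information from independent patients. Its standard error is then too small and it rejects a true null hypothesis more often than 5%. The plan states this principle and then specifies a primary test that does not follow it. A false positive would matter, because Study Design says the results will inform full conversion to a more expensive product.

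A design effect in the sample size does not protect the test. It adds patients but leaves the standard error used in the analysis uncorrected.

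**Working it through.** **Inputs from the documents.** Ratio of means 0.8, CV 1.1, two-sided 5%, 80% power, 251 per group, ICC 0.0001, about 100 per month, and 150 pilot cases in 6 months (all Sample Size Analysis); 302 patients in about one year (Interim Analysis).

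**The plan's sample size reproduces.** Log-scale variance = ln(1 + 1.1²) = 0.793 (SD 0.8905); difference = ln 0.8 = −0.2231. Then n = 2 × 0.793 × (1.960 + 0.842)² / 0.2231² = 250 per group. The noncentral t gives 251, with 80.0% power. The dispute is not with this figure.

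**Cluster size.** 150/6 = 25 per month; 302/12 = 25.2 per month; 502/25.2 = about 20 months.

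**True error of the patient-level test.** With independent month effects, DEFF = 1 + (m − 1) × ICC and error = 2 × [1 − Φ(1.96/√DEFF)]. Example: m = 25 and ICC 0.01 give DEFF = 1.24, 1.96/√1.24 = 1.760, error 7.8%. The month SD on the log scale is √(0.793 × ICC). ICCs above 0.0001 are assumed.

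| ICC | Month SD (log scale) | Error, 25 per month | Error, 100 per month |
|---|---|---|---|
| 0.0001 | 0.009 | 5.0% | 5.1% |
| 0.001 | 0.028 | 5.3% | 6.2% |
| 0.005 | 0.063 | 6.4% | 10.9% |
| 0.01 | 0.089 | 7.8% | 16.5% |
| 0.02 | 0.126 | 10.7% | 25.6% |
| 0.05 | 0.199 | 18.6% | 42.2% |

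**Simulation, 20 months of 25.** Results are for ICC 0.01, 0.02 and 0.05 (20,000 trials for the t-test, 6,000 for Wilcoxon).

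- Months randomized, independent month effects: t-test 8.0%, 10.6%, 18.4%; Wilcoxon 8.0%, 10.1%, 17.3%; t-test on month means 4.8–4.9%.
- Strict alternation, independent month effects: t-test 7.7%, 10.6%, 18.7%.
- Strict alternation, purely smooth 12-month seasonal effect: t-test 5.1%, 5.1%, 4.8%. The month-means test is then conservative (3.1%, 1.9%, 0.4%).

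**Could data settle the ICC?** SE(ICC) = √[2(1 − r)²(1 + (m − 1)r)² / (m(m − 1)(k − 1))]. At r = 0.0001 and m = 25, the pilot (k = 6) gives 0.026 and the trial (k = 20) gives 0.013. Neither could separate 0.0001 from 0.01, and the pilot could not separate it from 0.02.

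**Power when month is respected (10 v 10 months of 25, 18 df).** The variance of a month mean is 0.793 × [ICC + (1 − ICC)/25]. At ICC 0.01 this is 0.0393, so the SE of the difference is √(2 × 0.0393/10) = 0.0887, the noncentrality is 0.2231/0.0887 = 2.52, and power is 66%. The mixed-model figures come from 400,000 draws (REML truncated at zero).

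| ICC | Month-means power | Mixed-model power | Mixed-model error |
|---|---|---|---|
| 0.0001 | 75% | 73.7% | 3.6% |
| 0.005 | 71% | 69.6% | 4.1% |
| 0.01 | 66% | 65.6% | 4.5% |
| 0.02 | 59% | 58.4% | 4.8% |
| 0.05 | 43% | 43.2% | 5.0% |

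**The case against.** The strongest reply is that the harm is conditional. Nothing in the documents shows a month ICC above 0.0001, and at 25 per month the error is still only 5.3% at 0.001. The plan also gives a qualitative reason to expect a small ICC: one centre working to standard institutional procedures. That stands as a reason for hope, but it is not an estimate.

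The plan compares MELD and EUROSCORE between groups and allows covariate-adjusted linear models, which could absorb some case-mix differences between months. But the adjustment is optional, is not the primary test, and would not cover other month effects.

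The figure of 100 per month may count every hospital patient with a cryo order, since Study Design defines the clusters that broadly. That is possible, although the sample-size text says subjects. If so, the 100-per-month column does not describe this trial and the 25-per-month column applies.

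The power figures assume an exact 10–10 split. If each month is randomized independently, that split has probability 17.6%, and average month-means power falls to about 73% at ICC 0.0001 and 64% at 0.01. Study length is also inconsistent: one year in Study Design, two years in the inclusion criteria. Twelve months of 25 (6 v 6) would give only about 50% power at ICC 0.0001. Both points bear on the cost of the remedy, not on the need for it.

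Finally, not every secondary outcome is at patient level. Wastage per day and cost per month are not, and a linear-model month term does not carry over directly to the log-rank outcomes. The request is limited accordingly.

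**Conclusion.** The concern holds, with high confidence, and must be fixed. The primary test does not analyse by the unit randomized, and its nominal 5% depends on an ICC that the documents do not support. This is an unprotected assumption, not a test shown to fail: the excess is negligible at ICC 0.0001. At 25 per month the error becomes 7.8% at ICC 0.01 and 18.6% at 0.05, provided month effects are independent. A purely smooth seasonal pattern under strict alternation would cause no inflation. Because neither the pilot nor the trial can pin the ICC down, checking it afterwards cannot replace a test that is valid whatever its value.

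**What to change.** 1. Make the primary analysis a linear mixed model on log units, with product as fixed effect and month as random intercept, using Kenward-Roger or Satterthwaite degrees of freedom. Keep the month term whatever the estimated ICC, and report that ICC.
2. Use the same month term for patient-level secondary outcomes. For the time-to-event outcomes use an equivalent, such as a shared month frailty.
3. Before fixing the non-normal fallback, state whether months alternate or are re-randomized. If re-randomized, use a permutation test that follows the actual month randomization. If strictly alternating, only two sequences exist and a permutation test cannot reach p < 0.05, so use a month-level summary test. Pairing adjacent months avoids most of the seasonal conservatism (error 4.8%, 4.6% and 3.9% at ICC 0.01, 0.02 and 0.05).
4. Reconcile 25 with 100 subjects per month, and one year with two years.
5. Correct the ICC condition in the rationale from greater than 1 to greater than 0.

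The cost is SAP wording and one standard model, with no new data. The 80% power claim must be restated: about 74–75% near ICC 0 and 66% at 0.01 with 20 months of 25, or about 70% near ICC 0 if adjacent months are paired (9 df). The loss at higher ICCs reflects information the design lacks, and mainly more months, not more patients per month, would recover it. If accrual really were 100 per month, 502 patients would fill about 5 months (3 v 2, 3 df) and power would be about 47% even at ICC 0.0001, so the accrual figure should be settled first.

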The secondary outcomes, which are all routinely available in the EMR per standard of care, will include:

1. Number of cryo or fibrinogen concentrate products used perioperatively (defined as anesthesia start time to 3 days post-procedure)

- 2. Number of RBC, plasma, and platelet products used perioperatively (defined as anesthesia start time to 3 days post-procedure)
- 3. Time from OR start time to start of cryo transfusion
- 4. Time from cryo order to start of transfusion
- 5. Number of cryo units wasted by blood bank per month during study periods.
- 6. Laboratory measures, as available in the medical record, related to the indications for cryo: pre and post transfusion FIBTEM amplitude at 10 mins and maximum clot firmness & fibrinogen level within 10 minutes to one hour after the end of the first cryo transfusion.
- 7. Highest and lowest fibrinogen level or ROTEM FIBTEM within 24 hours after surgery.
- 8. Volume in drains (e.g. chest tube for CV surgery) at 24 hours or until removed, whichever is sooner.
- Time from end of bypass pump until end of surgery (reflects time to hemostasis) for CV surgery
- 10. Length of stay (OR, ICU and hospital)
- 11. Need for ventilator
- 12. Time on ventilator
- 13. Overall cost of cryo vs PR cryo, when factoring wastage, during each 1-month period
- 14. Adverse events: fevers, infections, transfusion reactions within 5 days of surgery start time, need for surgical re-exploration, multiorgan system failure
- 15. Fibrinogen level most proximal to end of procedure

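### The two lists of secondary endpoints disagree on the product-use window, the wastage unit and item 3, and nothing says which list governs

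*Combined protocol and SAP*

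**What the plan says.** The combined protocol and SAP lists 15 secondary outcomes under Study Design. Evaluation of Product Superiority then gives ten numbered secondary endpoints with tests. Both are current text.

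- **Product use (items 1 and 2 in both lists).** Study Design: "defined as anesthesia start time to 3 days post-procedure". Evaluation of Product Superiority: "defined as anesthesia start to 24 hours post-procedure".
- **Wastage (item 5 in both lists).** Study Design: "Number of cryo units wasted by blood bank per month during study periods". Evaluation of Product Superiority: "Number of cryo units wasted by blood bank per day during study periods", with a Wilcoxon rank-sum test.
- **Item 3.** Study Design: "Time from OR start time to start of cryo transfusion". Evaluation of Product Superiority: "Time from cryo order to ready in the blood bank".
- **Drain volume (item 8, then item 7).** Study Design: "Volume in drains (e.g. chest tube for CV surgery) at 24 hours or until removed, whichever is sooner". Evaluation of Product Superiority: "Volume in mediastinal drains (e.g. chest tube for CV surgery) at 24 hours (or until removed".

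The Holm procedure is applied to the secondary endpoints. The rationale for the cluster design says that one product is used hospital-wide for a whole calendar month.

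**The concern.** For product use, wastage and item 3, an analyst who follows one list departs from the other. As long as both versions stand, the choice can be made after the results are known. Holm adjusts for the number of endpoints tested; it does not adjust for choosing between two definitions of one endpoint.

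The endpoints are not peripheral. Study Design gives less use of other blood products and less wastage as the reasons for evaluating the new product before converting to it.

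The wastage unit also decides what counts as an observation. If each day is one, a rank-sum test treats the days of a month as independent although they share one assignment. If a daily rate is meant, calculated once per month, the test fits the design, but the plan does not say so.

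**Working it through.** **1. The plan's own sample size.** Inputs from Sample Size Analysis: ratio of means 0.8, coefficient of variation 1.1, two-sided 5%, power 80%. On the log scale the difference is |ln 0.8| = 0.2231 and the SD is √ln(1 + 1.1²) = 0.8905. Then n = 2 × [0.8905 × (1.960 + 0.842) / 0.2231]² ≈ 250 per group; the t-based solution is 250.96, that is 251. The stated figure reproduces. It concerns the primary endpoint and does not depend on anything below.

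**2. The lists side by side.**

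| Study Design | Evaluation of Product Superiority | Result |
|---|---|---|
| 1, 2 product use, to 3 days | 1, 2, to 24 hours | conflict |
| 3 OR start to cryo start | 3 order to ready | different endpoint |
| 4 order to start | 4 | agrees |
| 5 wastage per month | 5 wastage per day | conflict |
| 6 laboratory measures | 6 | same measures; sampling window not repeated |
| 7 highest/lowest fibrinogen or FIBTEM | none of its own | perhaps within 6 |
| 8 drains | 7 mediastinal drains | scope unclear |
| 9 bypass end to surgery end | none | no method |
| 10, 12 stay, ventilator time | 8 | agrees |
| 11 need for ventilator | none | no method |
| 13 monthly cost with wastage | 9 | agrees |
| 14 adverse events | none | no method |
| 15 end-of-procedure fibrinogen | 10 | agrees |

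**3. Wastage with days as observations.** Take m = 30 days per month and a within-month correlation ρ. The variance inflation is D = 1 + (m − 1)ρ, and the true error rate of a nominal 5% test is 2[1 − Φ(1.96/√D)] (normal approximation).

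| ρ | D | 1.96/√D | Error rate |
|---|---|---|---|
| 0.0001 | 1.0029 | 1.957 | 5.0% |
| 0.01 | 1.29 | 1.726 | 8.4% |
| 0.05 | 2.45 | 1.252 | 21% |

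The value 0.0001 is the one assumed in Sample Size Analysis, but there for the primary outcome. The other two are my assumptions. The documents give no correlation for wastage.

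**4. Choosing between the two windows.** If the smaller p of the 24-hour and 3-day tests were reported, the error rate would be 1 − P(|Z₁| < 1.96, |Z₂| < 1.96), which is 6.5%, 7.0% or 8.4% for assumed correlations of 0.95, 0.9 or 0.7 between the test statistics. At a threshold of 0.005 the same calculation gives 0.69%, 0.76% or 0.90%. This is an illustration; nothing in the documents suggests that such a choice is intended.

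**5. Power of a monthly wastage analysis.** The number of months is 12 (one year, Study Design), about 20 (502/302 × 12 = 19.9, from the accrual in Interim Analysis) or 24 (two years, Inclusion criteria). Holm's first threshold is 0.05/10 = 0.005 if the ten items are ten tests. If items 6 and 8 are split into three and four measures, there are 8 + 3 + 4 = 15 tests and the threshold is 0.05/15 = 0.0033. Power of the exact Wilcoxon test, simulated for an assumed shift of 1.5 SD of monthly wastage (normal data):

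| Months per arm | p ≤ 0.05 | p ≤ 0.005 | p ≤ 0.0033 |
|---|---|---|---|
| 6 | about 58% | about 21% | about 12% |
| 10 | about 85% | about 50% | about 44% |
| 12 | about 91% | about 65% | about 60% |

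With 12 months the smallest possible two-sided p is 2/C(12,6) = 0.0022 at a 6/6 split and 2/C(12,3) = 0.0091 at 9/3. The latter cannot pass Holm's first step.

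**The case against.** The best reply is that the list in Evaluation of Product Superiority is complete in itself: each of its ten items has a variable and a test, so an analyst can run it without the other list. That stands. A reader might infer that the secondary analysis cannot be run at all, and the documents do not support that. What remains is that the other list is equally current and the choice between them is open.

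Three further inferences are tempting and go too far.

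- *That drain volume is a conflict of the same rank.* Both lists give the same chest-tube example and the same 24-hour-or-removal limit, and nothing says that liver transplant drains are to be measured. The extra word may be loose wording, so it calls for a question only.
- *That every unmatched outcome lacks a method.* The laboratory item in the analysis list also concerns fibrinogen and FIBTEM, so it may cover the highest and lowest values. Time from bypass end to surgery end, need for ventilator and adverse events have no entry, but that is missing detail, which descriptive reporting could settle.
- *That the wastage test is known to be too liberal.* At ρ = 0.0001 the error is negligible, and a negative correlation would make D less than 1 and the test conservative. The calculation shows sensitivity to an unknown; it does not show an established error.

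It is also fair to say that this is a single-center pilot done as quality improvement, and that only secondary endpoints are involved. Some pages were removed before review and two figures in the analysis section are not shown, so a statement of precedence could exist there, though nothing suggests it.

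**Conclusion.** The concern holds in a limited form. Two definitional contradictions (product-use window, wastage unit) and one substituted endpoint (item 3) are plain on the page, and no available text resolves them. The comparison of the lists needs no assumptions and is firm.

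The numerical consequences are conditional. For wastage the error rate of a nominal 5% test runs from about 5.0% to 21% over assumed within-month correlations of 0.0001 to 0.05, and only if days are the observations. The cost of an open choice of window depends on a correlation that the documents do not give.

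The primary endpoint, the 251 per group, the order-to-start interval and the monthly cost comparison are untouched. This should be corrected before analysis, but it does not threaten the trial's main conclusion.

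**What to change.** Before any comparative data are seen, merge the two lists into one, with a single definition per endpoint.

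1. The sponsor chooses the product-use window and the item 3 interval. Any alternative that is kept is labelled a sensitivity analysis.
2. Analyse wastage with one value per calendar month, either a total or a daily rate. This matches the Study Design wording and the monthly cost comparison. A daily analysis that accounts for month would also respect the assignment.
3. State whether items 6 and 8 of the analysis list count as one test or several under Holm.
4. Clarify three minor points: whether the word mediastinal is meant to leave out liver transplant drains; whether item 6 covers the highest and lowest fibrinogen or FIBTEM; and whether the three outcomes without an entry are tested or descriptive.

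The change is to wording only. Its price is that wastage rests on about 12 to 24 monthly values. As step 5 of the working shows, power is then low, especially at Holm's early thresholds. The sponsor should accept this openly when the monthly unit is fixed.
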